Building on the efficacy of the CDC's Project Connect Health Systems Intervention to link heterosexual adolescents to competent comprehensive sexual health care services, we developed *Get Connected* (GC), an online brief intervention that employs individual and systems-level tailoring technology to reduce barriers to HIV prevention care (e.g., HIV/STI testing, PrEP) for YMSM. The deployment of GC through a mobile-friendly WebApp seeks to optimize online interventions' acceptability, accessibility, availability, and long-term affordability among youth. GC was developed for YMSM (ages 15-24) through a community-based participatory research approach that included a rapid assessment of existing HIV services through a mystery shopper methodology, and the creative input of scientists, service providers, and YMSM. Data from our pilot RCT (N=130 YMSM; ages 15-24) indicated high acceptability and feasibility for GC, and clinically meaningful effect sizes (ES) in self-efficacy to discuss HIV testing with partners (ES=.50-.64), trust in their providers (ES= .33-.35), reductions in number of sexual partners (ES=.21), and HIV/STI testing behavior (ES=.34; 30% of participants tested for HIV/STIs) at the 30-day post-intervention follow-up.

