## 2.0 STUDY OBJECTIVES

As part of the U19 project, we propose to test the efficacy of Get Connected (GC) for increasing HIV-negative or sero-status unaware YMSM's successful uptake of HIV and STI testing willingness (HIV and STI testing). Given the overall low level of PrEP awareness and use among YMSM currently, we also include awareness of and willingness to use PrEP as a primary outcome (PrEP uptake during the trial will be measured as a secondary outcome). At the agency level, HIV/STI testing sites listed in GC will receive biannual performance assessments based on ratings that YMSM provide after visiting their locations. We will examine improvements in the quality of HIV test counseling and PrEP-related referrals to YMSM accessing local HIV/STI testing sites in the 3 cities selected to test GC.

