### 3.0 STUDY DESIGN

#### 3.1 Study Phases

In this four-year study, we will enroll 480 self-reported HIV-negative or sero-status unaware, sexually active YMSM (ages 15-24) across three sites and randomize them into the GC intervention condition or to an attention-control condition. Primary outcomes will include (1) use of HIV prevention services (HIV testing, STI testing) and PrEP awareness and willingness. As secondary outcomes, we will assess PrEP use, sexual risk behaviors, and the linkage and retention in care among newly diagnosed HIV+ cases. We will also examine changes in GC's theorized mechanisms of change, including YMSM's attitudes, norms, self-efficacy, and behavioral intentions to adopt HIV prevention services.

Control condition: Participants randomized to the control condition will have access to the site locator portion of the Get Connected website, which includes information on HIV prevention services. While the provision of a test locator is a form (albeit weak) of an intervention, we felt that withholding referrals to testing and care services would be unethical given YMSM's vulnerability to HIV and STIs. Furthermore, given the availability of search engines to locate HIV/STI testing sites, the test locator condition may be considered usual care. Nevertheless, by providing the testing site locator only, we will be able to test the effect of the GC intervention condition (i.e., user-tailored content focused on HIV/STI testing and PrEP referral and the linkage to high-quality agencies) against the usual care control condition.

Intervention condition: Using a consensus approach to conceptualize health behavior change, the model guiding GC synthesizes The Integrated Behavioral Model and Self-Determination Theory as the theoretical underpinnings of our intervention. These theories emphasize social cognitive factors that impact behavior change and have informed HIV interventions. Consistent with these theories, GC content follows motivational interviewing (MI) principles by focusing on resolving ambivalence about HIV prevention behaviors, increasing self-efficacy for change, and enhancing motivation moving toward action. The intervention was developed by customizing content based on YMSM's psychosocial and sexual

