## 4.0 ELIGIBILITY AND SCREENING

### 4.1 Primary Objective (RCT): Inclusion Criteria

- *Assigned male sex at birth and currently identifies as male*

- *Aged 15 to 24 years (inclusive) at time of screening*
- *Self-report as HIV-negative or sero-status unaware*
- *Speak and read English*
- *Not be on PrEP at time of enrollment*
- *Report having consensual anal sex with a male partner in the prior 6 months and/or report having not received HIV testing in prior 6 months*
- *Reside in Philadelphia, Houston, or Atlanta*
- *Access to internet*

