- Sexual Risk Behavior:* Sexual risk behavior will be assessed using the Sexual Practices Assessment Schedule used in previous online studies with YMSM to explore the number of occasions of different sexual acts (oral, anal; receptive, insertive) with three different types of partners (romantic interest, casual partner “hookup,” or friend with benefits), use of condoms during the past 3 months, and knowledge about partners' HIV status and PrEP use. Assessments ascertain sexual behaviors with male and female partners, and will be asked at each follow-up. At-risk sex will be defined as any anal intercourse without condoms and/or PrEP that occurs with a person of known positive or unknown sero-status. We will assess the number of partners with whom participants had “at-risk sex.”
- PrEP Awareness and Willingness:* The survey will contain a brief description of PrEP to orient the participant. Questions are adapted from recent studies of PrEP attitudes with YMSM. PrEP awareness will be a single item measure of whether the participant has heard of PrEP (yes/no/I don't know). PrEP willingness will be measured with an existing 8-item scale developed for YMSM to gauge likelihood of PrEP use across different conditions (e.g., partner types; experiencing potential side effects).
- Technology and Social Media Use:* Given the online interface of the intervention, we will include Pew Internet Survey questions regarding use of different devices, the number of hours spent online through each device, the reasons for social media use, sites commonly frequented, and extent to which the Internet supplements face-to-face interactions. We will also measure AMSM's frequency of use of social media to look for HIV or sexual health-related information, and their online partner-seeking behaviors

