### 6.1.2 On-study Evaluations/Measures

- *HIV Testing:* Follow-up surveys will repeat the HIV testing questions in each follow-up survey. The HIV testing outcome will be: the proportion of MSM tested for HIV two or more times at least 3 months apart in the 12-month follow-up period (“frequent tester”). As an additional analysis, we will also examine the proportions of participants who receive one HIV test.
  - Among self-reported newly diagnosed HIV+ cases, we will measure their linkage and engagement with appropriate medical care after initial diagnosis using criteria employed in prior ATN protocols with youth. We will define linkage as an HIV-related medical visit within 45 days of referral, and engagement as a second HIV-related medical visit within 16 weeks of initial visit. Onset of ART initiation, self-reported adherence to ART, and viral suppression are exploratory indicators, as we recognize that our follow-up period may not be a sufficient amount of time to see these changes.
- *STI Testing:* The STI testing outcome is defined as the proportion of YMSM tested for STIs at least once in the 12-month follow-up period. We will ask participants what STIs they have been tested for, the anatomic sites where they were tested, the date of their most recent STI test (if known), and whether a medical provider had diagnosed them with an STI. In the follow-up surveys, we will ask participants whether they had been tested for STIs in the past 3 months (for the 1-month follow-up survey, we ask about the past 30 days). If STI testing is reported, we will ask participants to indicate what tests they received, and whether they were diagnosed with an STI by a medical provider.
- *PrEP Use:* At each follow-up assessment, PrEP-eligible HIV-negative YMSM (per CDC guidelines) will be asked whether they have begun using PrEP. We will also ascertain if a provider recommended PrEP and/or were offered a prescription for PrEP.
 

*Site Evaluations:* Across both trial arms, YMSM who report testing in the prior 3 months will complete self-evaluation forms of their testing experiences to assess comfort, quality, and concerns after visiting a site for HIV/STI testing and PrEP prevention services. The assessment form is the same form used by the mystery shoppers. We will use these data to update the WebApp and to send aggregate data of YMSM's satisfaction with services to agencies biannually.

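### PrEP use is asked only of participants classed PrEP-eligible and HIV-negative, with no fixed eligibility date or denominator, so the natural reading compares the arms on a post-randomisation subset

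*Combined protocol and SAP*

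**What the plan says.** Section 2.0 ranks the outcome: "PrEP uptake during the trial will be measured as a secondary outcome". Section 3.1 lists it next to sexual risk: "As secondary outcomes, we will assess PrEP use, sexual risk behaviors, and the linkage and retention in care".

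Section 6.1.2 gives the only measurement rule: "At each follow-up assessment, PrEP-eligible HIV-negative YMSM (per CDC guidelines) will be asked whether they have begun using PrEP". The CDC criteria are cited but not listed.

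Section 4.1 requires participants to "Not be on PrEP at time of enrollment" and to "Self-report as HIV-negative or sero-status unaware". Its risk criterion can be met by recent anal sex, by no recent HIV test, or by both, so entry does not itself require recent sexual risk.

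Section 2.4 commits the primary analyses to intention to treat with all randomised participants. Section 10.1.1 repeats the primary regressions for secondary outcomes without naming a denominator for PrEP use.

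Section 6.1.1 brings PrEP into a second outcome: "At-risk sex will be defined as any anal intercourse without condoms and/or PrEP".

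**The concern.** A filter on who is asked an outcome question is harmless if it is fixed before randomisation. It is not harmless if it depends on what participants do or report afterwards and the intervention can change that. The men asked in one arm are then no longer the counterparts of the men asked in the other. A difference can appear with no effect on PrEP starts, or a real effect can be inflated or diluted.

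The plan offers no safe default for the men who are skipped. Treating them as outside the analysis gives the subset comparison. Coding them as non-users loses any starter who falls outside the filter when asked. Treating them as missing sends them to section 10.4, which allows complete-case analysis or several forms of imputation. If the repeated-measures GEE of section 2.4 were used, its stated condition that data be missing completely at random would not hold for answers skipped because of reported behaviour or serostatus.

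At stake is the interpretation of one secondary outcome. The answers may also be unrecoverable once the surveys have been completed without the question.

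**Working it through.** **1. The plan's own figure.** None is given for PrEP use. Section 10.2.1 gives 400 participants for a 13-point difference in proportions such as HIV testing and PrEP awareness, with no control rate. A pooled two-sided test at 0.05 with 80% power gives N = 400 at 25% against 38%, so the figure is attainable but cannot be confirmed. It is used here only for 200 retained per arm (400/2).

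**2. Can the filter depend on arm?** The documents give these routes.

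- *Serostatus.* Men unaware of their status may enrol (4.1), and GC aims to raise testing (2.1). Known HIV-negative status and new positive diagnoses can therefore diverge by arm. A positive report ends participation (8.4.5). This route does not depend on the content of the CDC criteria.
- *Risk.* Section 1.2.3 reports for the pilot "reductions in number of sexual partners (ES=.21), and HIV/STI testing behavior (ES=.34; 30% of participants tested for HIV/STIs". If eligibility depends on reported risk (an assumption, since the criteria are not listed), GC can change it.
- *Entry.* Men admitted without recent sexual risk could become eligible later.

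Section 5.4.1 uses one survey for both arms. That does not help, because the filter acts on answers given after randomisation.

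**3. Illustration with no true effect.** Let u be the share of all participants who start PrEP, equal in both arms, and e the share asked. If every starter is among those asked, the rate among those asked is u/e. All values of u and e are assumptions. With u = 10% and control e = 50%:

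| GC share asked | Control rate | GC rate | Difference among those asked | Difference among all |
|---|---|---|---|---|
| 60% | 0.10/0.50 = 20.0% | 0.10/0.60 = 16.7% | -3.3 points | 0 |
| 70% | 20.0% | 0.10/0.70 = 14.3% | -5.7 points | 0 |
| 40% | 20.0% | 0.10/0.40 = 25.0% | +5.0 points | 0 |

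**4. Range.** Take control e of 50-70%, u of 5-15% and 200 retained per arm.

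- GC share 5-10 points higher: spurious differences from -0.5 to -5.0 points, with rejection probability 0.053 to 0.133 for a pooled Z-test at nominal 0.05.
- GC share 5-10 points lower: +0.6 to +7.5 points, with rejection probability 0.054 to 0.186.

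**5. Illustration with a true effect.** Let 10% of controls and 20% of GC start PrEP, a true risk ratio of 2.00, with control e = 60%. The control rate among those asked is 0.10/0.60 = 16.7%.

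- GC e = 50%: 0.20/0.50 = 40.0%, ratio 2.40.
- GC e = 70%: 0.20/0.70 = 28.6%, ratio 1.71.

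**6. The opposite assumption.** Suppose instead that all eligible men start at 20%, including the extra ones in GC, with e = 50% against 60%. Those asked show 20% against 20%. Among all randomised the rates are 0.50 × 0.20 = 10% and 0.60 × 0.20 = 12%. The spurious gap disappears, but a 2-point difference among all is now hidden.

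**7. Coding skipped men as non-users.** If a share m of starters is never asked while on PrEP, the recorded rate is u × (1 - m). This equals u only when m = 0, and it distorts the comparison when m differs by arm.

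**The case against.** The strongest reply is that section 6.1.2 says when men are asked, not when eligibility is set. A flag fixed at baseline fits the sentence and would remove most of the problem, leaving only the HIV-negative condition. Likewise, no section says that the analysis is confined to those asked. Both points stand: re-assessment at each visit and a subset analysis are natural readings, not stated rules. The plan adopts no alternative, however, and following the sentence as written leaves PrEP status unrecorded under this item for the men who are skipped.

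The illustration is also open to challenge. It places every starter among those asked, and the eligibility shifts have no source in the documents. With five follow-ups, a man eligible at any one of them may be captured, so a single-visit share overstates the exclusion. The headline case is far from significance: 20/100 against 20/120 gives Z of about 0.64. The pilot's fewer partners would suggest lower eligibility under GC, the reverse of that case. All of this stands, and it is why no size or direction is claimed.

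A reader might infer that the plan contradicts its intention-to-treat statement. It does not: section 2.4 applies that statement to the primary analyses, and PrEP use is secondary. The rule departs from the principle without breaching the text.

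A reader might also infer that at-risk sex will be misclassified. The definition in section 6.1.1 does not say whose PrEP use counts, and the same item also collects what each man knows of his partners' PrEP use. If eligibility follows reported risk, men having at-risk sex are also those most likely to be asked. This is a supporting point only.

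Finally, uptake among men with an indication is a legitimate question. It is properly answered in a subgroup defined at baseline.

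**Conclusion.** The concern holds as a flaw in how one secondary outcome is measured. The question is restricted by conditions that, on the natural reading, are assessed after randomisation and can be moved by the intervention, and no eligibility date, counting rule or denominator repairs this. The effect on the result could be negligible or a few percentage points in either direction; the figures above rest wholly on assumed eligibility shares and start rates. The conclusion itself needs only that eligibility or known HIV-negative status be current at follow-up and open to influence by GC. The primary HIV-testing comparison is not touched. The change is worth making because section 4.1 admits nobody already on PrEP: every randomised man can be counted as a potential starter, so the main comparison needs no subset.

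**What to change.** - Remove the eligibility filter: ask every participant still in follow-up about PrEP use at each follow-up survey.
- State in section 10 that PrEP initiation is analysed with all randomised participants as the denominator, and how men with no follow-up answer are handled. Section 3.1 projects 20% attrition, and participants who report an HIV-positive diagnosis are discontinued under 8.4.5.
- If an analysis among PrEP-eligible men is wanted, define eligibility from baseline data and report it as a subgroup.
- State in section 6.1.1 whose PrEP use enters the at-risk-sex definition.

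The cost is one added question for some participants, a few sentences in the plan, and a minor protocol modification reviewed by the IRB (section 11.4). If surveys have already been fielded with the filter, the final survey could ask everyone about any PrEP start since enrolment. That would recover part of the missing information, subject to recall.

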### 6.1.3 Premature Discontinuation/Off-Study Evaluations/Measures

RCT participants who request voluntary withdrawal and discontinue study participation after the Baseline survey but prior to the completion of the final survey at 12 months will be contacted by SRV staff in an attempt to understand the reason(s) for the participant's withdrawal and to potentially improve the service experience of the study and refine procedures.

Participants who are prematurely discontinued by a study PI or SRV staff will not be allowed to re-enroll into the study. Reason(s) for study discontinuation will be recorded through a CRF.

## 7.0 DATA COLLECTION AND SITE MONITORING

### 7.1 Development of Protocol and Case Report Forms

The Protocol Team in collaboration with the Management Core and Analytic Core, is responsible for the development of this protocol as well as the Case Report Forms (CRFs) needed to collect the information required to implement this protocol.

### 7.2 Data Records

Participant-related study information will be identified through a study ID number (SID) on all participant CRFs, audio files, transcripts, and Computer Assisted Self Interviewing (CASI) files. Participant names or other personally-identifying information will not be used on any study documents and will be redacted from interview transcripts. Participant names and their SID will be stored separately from other study information in SMART, accessible only to designated study staff, iTech site monitors, and representatives from the NICHD. SIDs will not be entered into the WebApp; instead, a unique WebApp ID will be assigned to each participant when they create an account for the WebApp. These unique WebApp IDs will be provided by the developer. Original source documents for individual participants will be maintained at the respective SRV and will be accessible only to the study staff. Data from original source documents will be transcribed on CRFs as applicable.

### 7.3 Data Collection

#### 7.3.1 CRFs

Study monitoring data, including untoward effects will be collected on CRFs. All CRFs for this study will be [completed](#) through iDataFax, an electronic CRF system.

#### 7.3.2. Mystery Shopper Data

For the second objective, mystery shopper participants will video chat, audio chat, or chat in-person with a study team member about every site visit, following the visit(s). If a video chat occurs, the BlueJeans platform will be used. These conversations are designed to give mystery shoppers an opportunity to discuss and process their visit and any notable incidents at a point when the visit is very recent and easily memorable. If any troublesome or adverse events are reported to the study team member, the study team member can provide the participant with support and external services, in addition to documenting the incident.

After each visit, Mystery Shoppers will complete a brief evaluation of the site using a web-based CASI at the SRV. All survey data will be collected using Qualtrics. Data will remain confidential; no personal identifying information will be collected during the computer session. The participant's unique SID# will be used in order to link the interview responses to the participant's CRF data. We will download the data directly from the administrative web application interface and manage it using Microsoft Excel. The data collected will be stored in a database held within a University of Pennsylvania secure server.

### 7.3.3 CASI Data

Data collected using a web-based CASI method will be on a portable computer, tablet, or mobile phone via an internet-based application. All survey data will be collected using SurveyGizmo. Data will remain confidential; no personal identifying information will be collected during the computer session. The participant's unique SID# will be used in order to link the interview responses to the participant's CRF data.

Self-administered surveys will be done at baseline and months 1, 3, 6, 9, and 12. They will be completed by participants on personal devices or laptop or desktop computers via surveys hosted on SurveyGizmo.com. We use SSL encryption for transfers of information online and data will be stored in the secure, HIPAA-compliant servers of SurveyGizmo. The Emory AC team maintains a business partner HIPAA agreement with SurveyGizmo.

### 7.3.4 CASI Data Security

To ensure data privacy, as soon as data is entered (in real-time), it will be encrypted during transmission to the AC using Secure Socket Layer (SSL) technology. The data will then be immediately stored in a secure database on an AC server within the AC data center.

The survey data collected through SurveyGizmo utilizes Amazon Web Services servers for hosting, located in controlled data center facilities in Boulder, Colorado. We clean, manage, and download the survey data directly from the SurveyGizmo application interface. The survey data collected through SurveyGizmo is encrypted while in transfer using SSL certificates, encrypted at the disk level in the Amazon Web Services database servers, and encrypted at the row level. Access to the SurveyGizmo account where the data can be downloaded is password-protected with a sufficiently complex password. The data collected through our web application is encrypted while in transfer using SSL certificates and access to the administrative web application where the data can be downloaded is password-protected using sufficiently complex passwords for each approved user.

